5.1.2 Sensitivity analysis

5.1.2.1 Per-protocol analysis of the primary outcome

A supportive analysis of the primary outcome will also be performed on the per-protocol population. Statistical methods will be the same as used in Section 5.1.1.

5.1.2.2 Covariate adjusted analysis of the primary outcome

An analysis of the primary endpoint will be adjusted for baseline information including age, body mass index (BMI), gender and complete or incomplete KD (following the KD diagnostic criteria from the American Heart Association released in 2017). From the above model, the adjusted estimates of RD and two-sided 95% CIs will be derived. The OR and RR with their 95% CIs will also be estimated from the GEE model using logit and log link function as described in Section 5.1.1.

Given the GEE model in the primary analysis has converged, if the GEE model doesn't converge when all covariates are introduced into the model simultaneously, the adjusted model will be established by removing a covariate one by one until the model converges.

5.1.2.3 Accounting for cluster effects of trial sites

A separate GEE model was applied to account for the cluster effects of trial sites, using the statistical method as described in Section 5.1.1. The RD with its 95% CI were estimated.

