3.4 Randomization and Blinding

Randomization is stratified by trial sites and done in block size of 4. According to the random seeds, a sequence of study numbers and allocation plan will be generated by the SAS software (version 9.4). Each allocation sequence will be placed in four small, opaque and sealed envelopes numbered in order from 1 to 4, and then enclosed in a larger, opaque and sealed envelope marked with the block number. The randomized plan and concealed envelopes will be prepared by an independent statistician team from the Clinical Trial Unit (CTU) of the Children's Hospital of Fudan University, and delivered to and kept by the site coordinate nurse. Recruited patients will be randomly allocated in a 1:1 ratio to the control or experimental group based on the randomization plan. At each site, after obtaining signed informed consent from the eligible participant, the trained physician will meet with the prespecified institutional nurse to achieve the allocation plan as indicated by the corresponding envelope. The coordinate nurse will open the envelopes in numbered order according to the enrollment order, reveal the treatment allocation to the physician, and record the assignments of the enrolled patient.

Patients and physicians who treat patients will not be masked to the allocation, while pediatric cardiologists who assess CAL by echocardiography will be blinded to the allocation. All researchers conducting outcome assessments will be masked in the trial. The trial statistician will also be blinded regarding the treatment code when developing the statistical analysis plan and writing the statistical programs, which will be validated and completed using dummy randomization codes. The actual allocation will only be provided to the study team after lock of the database.

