5.1. Primary Outcome Analysis

5.1.1 ITT analysis of the primary outcome - the primary analysis

The primary analysis will be based on the ITT population as defined above. The primary outcome is a binary outcome: CAL occurs or not within 1 month of illness onset. Since CAL will be repeatedly examined at enrollment, 2 weeks, 1 month, 3 months, 6 months and 12 months respectively, generalized estimating equation (GEE) model will be performed, with treatment, visit and interaction between treatment with visit as fixed effect, patient ID as cluster effect, the mean of 5 coronary artery baseline z scores (described in section 2.2.1) as covariate variable. Risk difference (RD) and two-sided 95% confidence intervals (CI) between the two treatment groups will be estimated from the model using a binomial distribution and identity link function. OR with 95% CI at each time point will be obtained using GEE model with binomial distribution and logit link function. Binomial distribution and log link function will be used to obtain estimation of risk ratio (RR) and 95% CI. Exchangeable correlation structure is assumed for within-group variation for all the GEE models. The P value for the interaction term will be used to determine the statistical significance of the group difference at specific time point.

If the above GEE model does not converge, a poisson distribution will be used for the family function. A negative binomial distribution will be subsequently used for family function in case the GEE model based on poisson distribution does not converge. RD, OR and RR with their 95% CI

estimates will be reported by using identity, logit and log link function, respectively. In the final analysis, a normal family distribution was used because none of the three prespecified distribution models converged. RD and 95% CI estimates were derived using identity link function.

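### Randomization is stratified by site but the primary GEE leaves site out, so the confidence interval for the primary risk difference is slightly too wide

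*SAP*

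**What the plan says.** Section 3.4 of the SAP sets the design: "Randomization is stratified by trial sites and done in block size of 4". Allocation is 1:1, and section 3.1 says that children are randomized individually. Site is the only stratification factor named.

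Section 5.1.1 specifies the primary model "with treatment, visit and interaction between treatment with visit as fixed effect, patient ID as cluster effect", and adds "the mean of 5 coronary artery baseline z scores (described in section 2.2.1) as covariate variable". Site does not appear. Footnote a to Table 2 in section 6.2 confirms that the baseline z score is the only covariate. On the model finally fitted, section 5.1.1 reports that "a normal family distribution was used because none of the three prespecified distribution models converged"; the risk difference came from the identity link.

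The covariate-adjusted analysis in section 5.1.2.2 uses "baseline information including age, body mass index (BMI), gender and complete or incomplete KD", again without site. The GLM in section 5.1.2.10 has no covariates at all.

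Site appears once, in section 5.1.2.3: "A separate GEE model was applied to account for the cluster effects of trial sites". That section refers back to 5.1.1 for its method. The note closing section 5.1.2.10 places analyses 5.1.2.3 to 5.1.2.7 at the manuscript stage, so the only analysis that uses site is post hoc.

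**The concern.** Blocks of four within site keep the arms nearly equal at every site. Differences in CAL risk between sites then largely cancel from the treatment contrast. An analysis that ignores site does not know this and still counts the between-site variation in its standard error. The interval is wider than the design warrants, and the test runs below its nominal 5% level.

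What is at stake is precision. Section 3.5 sizes the trial for 80% power on a difference of 3.3 points, so there is little reason to give any of it away.

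Section 5.1.2.3 is not a clear substitute. Children, not sites, are randomized, and both arms occur at every site, so site is a stratum rather than a unit of randomization. The section does not say whether site replaces patient as the GEE cluster, is added to it, or enters in some other way.

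**Working it through.** **Inputs from the SAP (section 3.5).** CAL risk 12.4% (control) and 9.1% (experimental), two-sided alpha 0.05, power 0.80, 1,400 per arm before dropout.

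**Inputs assumed.** The text available gives neither the number of sites nor the variation in CAL risk between them. I take a between-site SD of 3, 5 or 7.4 percentage points and, in the simulations, 28 sites.

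**1. The plan's own figure.** The two-proportion formula gives 1,382 per arm, or 1,442 with continuity correction. The stated 1,400 is reproduced and does not depend on this point.

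**2. Standard error without site.**

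- Variance sum: 0.124 × 0.876 + 0.091 × 0.909 = 0.19134.
- SE = √(0.19134 / 1,400) = 0.01169.
- 95% half-width = 1.96 × 0.01169 = 2.29 points.

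**3. Standard error with site as a stratum.** Let ρ be the share of outcome variance that lies between sites. The mean risk is (0.124 + 0.091)/2 = 0.1075, so ρ = SD² / (0.1075 × 0.8925) = SD² / 0.09594. Then SE(stratified) = 0.01169 × √(1 − ρ), and the SE without site is too large by the factor 1/√(1 − ρ).

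| Between-site SD (points) | ρ | SE stratified | SE without site too large by | Half-width with site (points) | Actual type I error without site | Power without / with site |
|---|---|---|---|---|---|---|
| 3 | 0.009 | 0.01164 | 0.5% | 2.28 | 0.049 | 80.7% / 81.0% |
| 5 | 0.026 | 0.01154 | 1.3% | 2.26 | 0.047 | 80.9% / 81.6% |
| 7.4 | 0.057 | 0.01135 | 3.0% | 2.23 | 0.044 | 81.3% / 82.8% |

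**4. Simulation of the same contrast.** With 2,800 children, 28 sites, stratified blocks of four and 6,000 trials per setting, the mean reported SEs without and with site were 0.01169 and 0.01165, 0.01169 and 0.01158, and 0.01179 and 0.01153. The SE without site is too large by 0.4%, 1.0% and 2.2%. The gain in power from including site was 0.2 to 1.3 points, slightly below the formula's 0.3 to 1.5. The empirical SDs of the two estimators were identical, so the excess lies in the reported SE and not in the estimate. The stratified interval covered 94.8% to 94.9%.

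**5. Sensitivity to the number of sites.** A separate simulation with 10, 20 or 28 equal sites (20,000 runs each) gave type I error without site of 0.042 to 0.047 at ρ = 0.05 and about 0.040 at ρ = 0.10. The stratified SE kept it at 0.048 to 0.053. Direction and size hardly depend on the site count.

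**6. If site were the GEE cluster.** With 28 equal sites, 2,800 children and 3,000 runs per setting, the SEs were:

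| Between-site SD (points) | No site | Site as stratum | Site as sandwich cluster |
|---|---|---|---|
| 3 | 0.01169 | 0.01164 | 0.01163 |
| 5 | 0.01168 | 0.01153 | 0.01157 |
| 7.4 | 0.01172 | 0.01140 | 0.01140 |

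The site-clustered variance therefore tracks the stratified one closely. Its intervals covered about 94% with equal sites and about 93% with unequal ones, because the variance rests on few clusters.

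None of these calculations includes the baseline z score.

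**The case against.** The strongest reply is that the effect is close to rounding error. Over the assumed range the half-width changes by about 0.01 to 0.07 points (2.29 against 2.28 to 2.23), beside a planned difference of 3.3 points, and the error is in the conservative direction. A 5% excess in width needs ρ = 0.10, a between-site SD of about 9.8 points around a mean risk of 10.75%, and nothing in the SAP supports that. The site count and the site variation are both assumed. The primary model also adjusts for mean baseline z score, which may already carry part of the difference between sites, so the gain may be overstated. All of this stands, and it limits the weight of the point.

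A second reply concerns feasibility. Under the assumed 28 sites, site indicators add up to 27 parameters to a model for which none of the three prespecified families converged. This stands for the binomial, Poisson and negative binomial families. It has little force for the normal family with identity link that was finally used, where site terms are ordinary linear terms, or for a Mantel-Haenszel risk difference, which needs no iterative fit.

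A reader might also infer that clustering on site fails to use the balance created by stratification. That is not so. With 1:1 allocation inside each site, the site effect cancels from that site's contribution to the treatment estimate, and step 6 shows nearly the same SE. The weakness of a site-clustered variance is the small number of clusters, which makes its intervals slightly too narrow. Nor does section 5.1.2.3 say that site replaces patient as the cluster. The fair criticism is that it leaves this open.

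**Conclusion.** The mismatch is real: site stratifies the randomization, is absent from the primary model, and enters only a post hoc model of unclear form. The consequence is a primary interval that is slightly too wide. The SE excess is about 0.4% to 3% and the power loss roughly 0.2 to 1.3 points, assuming 28 sites, a between-site SD of CAL risk of 3 to 7.4 points and no recovery through the baseline z score.

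A reader might conclude that the primary interval is invalid. The documents do not support that. On this point the risk difference is unbiased, coverage is at or a little above 95%, and the false-positive rate is not raised. This is a cheap refinement that brings the analysis into line with the design; it does not call the primary result into question.

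**What to change.** In section 5.1.1, include site as a stratification factor in the risk-difference model, keep patient as the GEE cluster, and state the rule by which small sites are pooled. If the site terms prevent convergence under the binomial, Poisson or negative binomial family, report the site-stratified Mantel-Haenszel risk difference at 1 month.

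In section 5.1.2.3, either state how site and patient clustering are combined and how the variance is estimated, or replace the analysis with the stratified one.

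Section 5.1.1 already reports how the final model was fitted, so the change should be labelled as made after that analysis, with the estimate without site shown beside it.

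The cost is up to one parameter per site, less one, and a pooling rule to define. The Mantel-Haenszel fallback would not adjust for baseline z score. No new data are needed.

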5.1.2.4 Best-case scenario

Participants with missing primary outcomes were assumed to have the best possible outcome, i.e., CAL did not occur at one month of illness onset in all of them. The statistical method was identical to that used in Section 5.1.1.

5.1.2.5 Worst-case scenario

Participants with missing primary outcomes were assumed to have the worst possible outcome, i.e., CAL occurred at one month of illness onset in all of them. The statistical method was identical to that used in Section 5.1.1.

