3.5 Sample Size

This study is a superiority trial. Sample size calculation is performed based on the difference of the primary outcome between the two arms. According to the previous study³, we assume a difference in the proportion of patients with CAL occurred within the first month of illness between the two groups of 3.3% (12.4% vs 9.1%, odds ratio [OR] = 0.73 for the control arm and the experimental arm, respectively). With an α of 0.05 and a power of 0.8, a sample size of 1400 cases in each group will be needed. With an assumed dropout rate of 10%, a total of 3200 patients are planned for recruitment (1600 per arm).

4. Analysis Populations

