4.1 Study Population Data Sets

Three study populations will be considered in the analysis. The primary analysis for the primary objective will be based on the intention-to-treatment population.

Intention-to-Treat population

Intention-to-treat (ITT) population will be defined at the moment the randomization is performed, including all subjects who are randomized.

Participants will be excluded from the ITT analysis if the primary outcome is missing, forming a modified ITT population (mITT).

Per-protocol population

Participants will be excluded from the per-protocol (PP) population if they:

- Being randomized but not receiving any treatment.

- Not adhering to allocated treatment due to:
 - aspirin allergy in either group.
 - being allocated to the experimental arm, while not completing the prednisolone treatment as recommended by the protocol (i.e., stopped early, took less than the recommended doses or tapered more quickly than the recommended period).
 - being allocated to the control arm but were prescribed additional prednisolone treatment due to discovered with IVIG resistance or other co-morbidities, such as juvenile idiopathic arthritis and necrotic lymphadenitis.

The treatment groups in the PP analysis will be determined according to what the participant actually received. This population will be used for the supportive analyses.

Safety population

Participants given any medicine-relate-treatments will be included in this population. Adverse reactions and events will be recorded. This population will be used for the safety analyses.

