5.1.2.10 GLM model analysis

This analysis used generalized linear model (GLM) treating response variable as a simple binary outcome without adjustment for any covariate. RD and 95% CI were estimated using a binomial distribution and an identity link function.

Sensitivity analyses 5.1.2.3 – 5.1.2.7 were conducted during manuscript preparation, and analyses 5.1.2.8 – 5.1.2.10 were added in response to reviewers' suggestions during manuscript revision.

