5.3 Handling of Missing data

Missing baseline covariates will be imputed using simple imputation methods in the covariate adjusted analysis based on the covariate distributions, should the missing values for a particular covariate be less than 5%. For a continuous variable, missing values will be imputed from random values from a permuted normal distribution with mean and SD calculated from the available sample. For a categorical variable, missing values will be imputed from random values from a uniform distribution with probabilities P1, P2, ..., and Pk from the sample. The seed to be used is 20230605. We do not assume the condition that missing of covariate variable at baseline will be over 5%.

6. General Considerations for Data Analyses

SAS (version 9.4) will be used to perform all data analyses and generate majority of data displays. STATA® (version 16.0) or R may also be used for some data analyses and generating statistical graphs. All analyses for the primary and secondary outcome variables will be primarily based on ITT population. Two-side tests and P values will be reported. Regression models for repeated measurement will be used for outcomes that are repeatedly measured, group differences at the prespecified timepoint will be computed and reported.

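### The best- and worst-case analyses give missing children in both arms the same outcome, so they neither test arm-specific risk among the missing nor bound the treatment effect

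*SAP*

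**What the plan says.** - **Population.** Section 5.1.1 states: "The primary analysis will be based on the ITT population as defined above". Section 4.1 first defines ITT as everyone randomized and then adds: "Participants will be excluded from the ITT analysis if the primary outcome is missing, forming a modified ITT population (mITT". The table shells in 6.2 carry the ITT label.
- **Checks on the missing outcome.** In the best case (5.1.2.4), for the children with a missing outcome, "CAL did not occur at one month of illness onset in all of them". In the worst case (5.1.2.5), "CAL occurred at one month of illness onset in all of them". Neither rule refers to treatment arm, and both use the method of 5.1.1.
- **Timing.** The closing note of 5.1.2.10 says analyses 5.1.2.3 to 5.1.2.7, which include both scenarios, "were conducted during manuscript preparation".
- **Other missing-data provision.** Section 5.3 concerns baseline data only: "Missing baseline covariates will be imputed using simple imputation methods in the covariate adjusted analysis". The remaining sensitivity analyses change the population, covariates, clustering, CAL definition or model, not the missing outcomes.
- **Masking.** Section 3.4: "Patients and physicians who treat patients will not be masked to the allocation". The cardiologists who read the echocardiograms are blinded.

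**The concern.** Excluding children without a one-month outcome is harmless only if, within each arm, those excluded resemble those kept. Families and treating physicians know the allocation, so the reasons for missing the one-month echo could differ by arm even when the missing rates are similar. Blinded reading does not protect against selective attendance.

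The sensitivity analyses should probe this, but a rule that assigns one value to all missing children, regardless of arm, largely cancels out of the treatment difference. It responds to a difference in how many children are missing. It cannot respond to a difference in how sick the missing children are. A reader who sees a best and a worst case that agree may conclude that the result is robust to missing data when that has not been tested.

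The exclusion also reaches further than it need. Read as an outcome at one month, it removes children who have a 2-week or 3-month echo, although those measurements could inform the missing value.

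**Working it through.** **Inputs.** From SAP 3.5: CAL risk 12.4% control (p_c) and 9.1% experimental (p_e), 1600 children per arm, 10% dropout. Assumed: missing proportions d_c and d_e of 2% to 10%, because the SAP gives none for the one-month echo. All figures use simple proportions with an unpooled Wald 95% CI, not the SAP's GEE. RD is experimental minus control in percentage points; negative favours prednisolone.

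**Plan's own figure.** The two-sided 5%, 80% power calculation for 12.4% versus 9.1% gives 1382 per arm (pooled variance), in line with the SAP's 1400. The planning rates are therefore a fair base for illustration.

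**Formulas.**
- Best case: RD = (1-d_e)p_e - (1-d_c)p_c.
- Worst case: the same expression plus (d_e - d_c).
- The CAL risk among the missing appears in neither. With d_e = d_c = d both reduce to (1-d)(p_e - p_c).
- Arm-opposed extremes at equal d: -3.3(1-d) ± 100d.

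**Equal missingness.**

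| Missing per arm | Best case | Worst case | Opposed, favourable | Opposed, adverse |
|---|---|---|---|---|
| 2% | -3.23 (-5.36 to -1.11), p=0.003 | -3.23 (-5.53 to -0.94), p=0.006 | -5.23 | -1.23 (-3.45 to +0.98) |
| 5% | -3.135 (-5.23 to -1.04), p=0.003 | -3.135 (-5.62 to -0.65), p=0.014 | -8.135 | +1.865 (-0.44 to +4.17) |
| 10% | -2.97 (-5.02 to -0.92), p=0.004 | -2.97 (-5.72 to -0.22), p=0.035 | -12.97 | +7.03 (+4.59 to +9.47) |

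At 10% missing the SAP's two point estimates span 0 points, while the extremes span 20.

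**Blind spot.** Suppose missing experimental children have 50% CAL and missing controls 12.4%.
- 5% missing: experimental 0.95×9.1 + 0.05×50 = 11.145; control 12.4; RD -1.255 (-3.49 to +0.98), p=0.27. Both SAP checks still show -3.135.
- 2% missing: experimental 0.98×9.1 + 0.02×50 = 9.918; RD -2.48 (-4.66 to -0.30), p=0.026, so significance is kept.

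**Unequal missingness.**
- 5% control, 6% experimental: the worst case is -2.23 (-4.74 to +0.29), p=0.083. Here the check does respond.
- 6% control, 5% experimental: best 0.95×9.1 - 0.94×12.4 = -3.01; worst -3.01 - 1.00 = -4.01. The worst case now favours prednisolone more than the best case does.

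**Tipping point.** Hold missing controls at 12.4% and solve (1-d)p_e + d·q - p_c + 1.96·SE = 0 for q, the CAL risk among missing experimental children. With 1600 per arm and the SE updated, q is 64.5% (2% missing), 31.2% (5%) and 20.2% (10%). Other SE conventions give 63-66%, 30-31% and 19-20%.

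**The case against.** The SAP never calls the pair bounds on the treatment effect. It defines best and worst as outcomes for the child, and on that meaning the labels are right. This stands: nothing in 5.1.2.4 or 5.1.2.5 is false as written. What fails is their use as the only checks on exclusion in a superiority comparison.

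The missing rate is unknown, and so is the observed effect. This also stands. At 2% missing the sign cannot change, and significance is lost only at an implausibly high risk among missing experimental children. If the observed rates were, say, 12.4% versus 11.0% with 5% missing, both checks would already be non-significant (p=0.23 and 0.31) and there would be nothing to tip. The figures show what the checks can and cannot detect; they do not predict the trial's result.

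The SAP's model is a covariate-adjusted GEE over repeated visits, finally with a normal family. Equality of the two RDs is then approximate rather than exact. Even with equal missing rates, the CIs, p-values, RR and OR of the two scenarios differ.

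Section 5.1.1 describes the outcome as CAL within one month, so a child with a 2-week echo might arguably not count as missing. However, 2.2.1, 5.1.2.4 and 5.1.2.5 all place the outcome at one month, which is the better-supported reading. The looser one would shrink the missing group but would not cure the same-value rule.

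Finally, the SAP gives no evidence that attendance differed by arm. That is so; the case rests on open-label treatment making it possible.

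**Conclusion.** The concern holds. No analysis in the SAP lets the CAL risk among children with a missing outcome differ by arm, and the best- and worst-case pair does not bound the treatment effect. The pair detects excess missingness in the experimental arm; it misses arm-dependent risk at similar missing rates, and it runs in the opposite direction when more controls are missing.

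The importance depends on the missing rate. At about 2% per arm the conclusion would probably survive any reasonable scenario. At 5% to 10% the tipping point falls to between about 31% and 20% CAL among missing experimental children, and the latter is not far above the 12.4% planning control rate. These sizes assume that the planning rates are observed, that 1600 children are randomized per arm, and that simple proportions approximate the model. The gap should be closed, but it does not invalidate the primary analysis. The ITT/mITT labelling is a minor point on its own.

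**What to change.** Keep the primary analysis and make these changes:

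1. In 5.1.1 and the table shells, name the primary population mITT.
2. In 5.1.2.4 and 5.1.2.5, describe the scenarios as same-value imputations, state that they are not bounds on the treatment effect, and report the number missing the one-month outcome by arm beside them.
3. Add arm-opposed scenarios on all randomized children: missing experimental children with CAL and missing controls without, and the reverse.
4. Add a tipping-point analysis that varies the CAL risk among the missing separately by arm. It may be built on multiple imputation using the baseline, 2-week and 3-month echoes.

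Label items 3 and 4 as post hoc. The cost is modest programming and a few sentences, with no new data. The arm-opposed extremes will be wide and are not plausible values in themselves, so the tipping point should carry the interpretation. If missingness proves low, it will demonstrate robustness that the present pair cannot.
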